### 6.3.1.2 General Exclusion Criteria

1. Any surgery requiring general anesthesia or discontinuation of aspirin and/or an ADP antagonist is planned within 12 months after the procedure.
2. Subject has known hypersensitivity or contraindication to device material and its degradants (everolimus, poly (L-lactide), poly (DL-lactide), lactide, lactic acid) and cobalt, chromium, nickel, platinum, tungsten, acrylic and fluoro polymers that cannot be adequately pre-medicated. Subject has a known contrast sensitivity that cannot be adequately pre-medicated.
3. Subject has known allergic reaction, hypersensitivity or contraindication to aspirin; or to clopidogrel and prasugrel and ticagrelor; or to heparin and bivalirudin, and therefore cannot be adequately treated with study medications.
4. Subject had an acute myocardial infarction (AMI: STEMI or NSTEMI) within 72 hours of the index procedure and both CK and CK-MB have not returned to within normal limits at the time of index procedure; or subject with stable angina or silent ischemia has CK-MB that is greater than normal limits at the time of the index procedure.
5. Subject is currently experiencing clinical symptoms consistent with new onset AMI (STEMI or NSTEMI), such as nitrate-unresponsive prolonged chest pain with ischemic ECG changes.
6. Subject has a cardiac arrhythmia as identified at the time of screening for which at least one of the following criteria is met:
  - a. Subject requires coumadin or any other agent for chronic oral anticoagulation
  - b. Subject is likely to become hemodynamically unstable due to their arrhythmia
  - c. Subject has poor survival prognosis due to their arrhythmia
7. Subject has a left ventricular ejection fraction (LVEF) < 30% assessed by any quantitative method, including but not limited to echocardiography, MRI, Multiple-Gated Acquisition (MUGA) scan, contrast left ventriculography, PET scan, etc. LVEF may be obtained within 6 months prior to the procedure for subjects with stable CAD. For subjects presenting with ACS, LVEF must be assessed during the index hospitalization (which may include during the index procedure by contrast left ventriculography) but prior to randomization in order to confirm the subject's eligibility.
8. Subject has undergone prior PCI within the target vessel during the last 12 months. Prior PCI within the non-target vessel or any peripheral intervention is acceptable if performed anytime >30 days before the index procedure, or between 24 hours and 30 days before the index procedure if successful and uncomplicated.

 Investigator should use discretion when enrolling subjects with high CHADS scores.

9. Subject requires future staged PCI either in target or non-target vessels or subject requires future peripheral interventions < 30 days after the index procedure.
10. Subject has received any solid organ transplants or is on a waiting list for any solid organ transplants.
11. At the time of screening, the subject has a malignancy that is not in remission.
12. Subject is receiving immunosuppressant therapy or has known immunosuppressive or severe autoimmune disease that requires chronic immunosuppressive therapy (e.g., human immunodeficiency virus, systemic lupus erythematosus, etc.). Note: corticosteroids are not included as immunosuppressant therapy.
13. Subject has previously received or is scheduled to receive radiotherapy to a coronary artery (vascular brachytherapy), or the chest/mediastinum.
14. Subject is receiving or will require chronic anticoagulation therapy (e.g., coumadin, dabigatran, apixaban, rivaroxaban or any other agent for any reason).
15. Subject has a platelet count < 100,000 cells/mm^3 or > 700,000 cells/mm^3.
16. Subject has a documented or suspected hepatic disorder as defined as cirrhosis or Child-Pugh  $\geq$  Class B.
17. Subject has renal insufficiency as defined as an estimated GFR < 30 ml/min/1.73m^2 or dialysis at the time of screening.
18. Subject is high risk of bleeding for any reason; has a history of bleeding diathesis or coagulopathy; has had a significant gastro-intestinal or significant urinary bleed within the past six months.
19. Subject has had a cerebrovascular accident or transient ischemic neurological attack (TIA) within the past six months, or any prior intracranial bleed, or any permanent neurologic defect, or any known intracranial pathology (e.g., aneurysm, arteriovenous malformation, etc.).
20. Subject has extensive peripheral vascular disease that precludes safe 6 French sheath insertion. Note: femoral arterial disease does not exclude the patient if radial access may be used.
21. Subject has life expectancy < 5 years for any non-cardiac cause or cardiac cause.
22. Subject is in the opinion of the Investigator or designee, unable to comply with the requirements of the study protocol or is unsuitable for the study for any reason. This includes completion of Patient Reported Outcome instruments.

 Estimated GFR can be based on Modification of Diet in Renal Disease (MDRD) equation or Cockcroft-Gault equation (CCG).

23. Subject is currently participating in another clinical trial that has not yet completed its primary endpoint.
24. Subject is part of a vulnerable population who, in the judgment of the investigator, is unable to give Informed Consent for reasons of incapacity, immaturity, adverse personal circumstances or lack of autonomy. This may include: Individuals with mental disability, persons in nursing homes, children, impoverished persons, persons in emergency situations, homeless persons, nomads, refugees, and those incapable of giving informed consent. Vulnerable populations also may include members of a group with a hierarchical structure such as university students, subordinate hospital and laboratory personnel, employees of the Sponsor, members of the armed forces, and persons kept in detention.

### **6.3.2 Angiographic Eligibility Criteria**

Assessment of angiographic eligibility is per visual assessment by an investigator both for qualitative and quantitative variables. IVUS, OCT or on-line QCA may be used if deemed necessary by investigators.

#### **6.3.2.1 Angiographic Inclusion Criteria**

1. One or two *de novo* target lesions:
  - a. If there is one target lesion, a second non-target lesion may be treated but the non-target lesion must be present in a different epicardial vessel, and must be treated first with a successful, uncomplicated result prior to randomization of the target lesion.
  - b. If two target lesions are present, they must be present in different epicardial vessels and both must satisfy the angiographic eligibility criteria.
  - c. The definition of epicardial vessels means the LAD, LCX and RCA and their branches. Thus, the patient must not have lesions requiring treatment in e.g. both the LAD and a diagonal branch.
2. Target lesion(s) must be located in a native coronary artery with a visually estimated or quantitatively assessed %DS of  $\geq 50\%$  and  $< 100\%$  with a TIMI flow of  $\geq 1$  and one of the following: stenosis  $\geq 70\%$ , an abnormal functional test (e.g. fractional flow reserve, stress test), unstable angina or post-infarct angina.
  - a. Lesion(s) must be located in a native coronary artery with RVD by visual estimation of  $\geq 2.5$  mm and  $\leq 3.75$  mm.
  - b. Lesion(s) must be located in a native coronary artery with length by visual estimation of  $\leq 24$  mm.

 This includes clinical trials of medications and invasive procedures. Questionnaire-based studies, or other studies that are non-invasive and do not require medication are allowed. A subject who is taking part in the long-term follow-up phase of a trial, who has completed all medications and invasive procedures per protocol requirements, may continue to participate in that trial.

c. For Lead-In subjects with 3.0x18 mm Absorb BVS: lesion(s) must be located in a native coronary artery with RVD by visual estimation of  $\geq 2.75$  mm and  $\leq 3.25$  mm. The lesion length by visual estimation is  $\geq 8$  mm and  $\leq 14$  mm.

### 6.3.2.2 Angiographic Exclusion Criteria

All exclusion criteria apply to the target lesion(s) or target vessel(s).

1. Lesion which prevents successful balloon pre-dilatation, defined as full balloon expansion with the following outcomes:
  - Residual %DS is a maximum of  $< 40\%$  (per visual estimation),  $\leq 20\%$  is strongly recommended.
  - TIMI Grade-3 flow (per visual estimation).
  - No angiographic complications (e.g. distal embolization, side branch closure).
  - No dissections NHLBI grade D-F.
  - No chest pain lasting  $> 5$  minutes.
  - No ST depression or elevation lasting  $> 5$  minutes
2. Lesion is located in left main.
3. Aorto-ostial RCA lesion (within 3 mm of the ostium).
4. Lesion located within 3 mm of the origin of the LAD or LCX.
5. Lesion involving a bifurcation with a:
  - a. side branch  $\geq 2$  mm in diameter, or
  - b. side branch with either an ostial or non-ostial lesion with diameter stenosis  $> 50\%$ , or
  - c. side branch requiring dilatation.
6. Anatomy proximal to or within the lesion that may impair delivery of the Absorb BVS or XIENCE stent:
  - a. Extreme angulation ( $\geq 90^\circ$ ) proximal to or within the target lesion.
  - b. Excessive tortuosity ( $\geq$  two  $45^\circ$  angles) proximal to or within the target lesion.
  - c. Moderate or heavy calcification proximal to or within the target lesion. If IVUS used, subject must be excluded if calcium arc in the vessel prior to the lesion or within the lesion is  $\geq 180^\circ$ .
7. Vessel contains thrombus as indicated in the angiographic images or by IVUS or OCT.

8. Lesion or vessel involves a myocardial bridge.
9. Vessel has been previously treated with a stent at any time prior to the index procedure such that the Absorb BVS or XIENCE would need to cross the stent to reach the target lesion.
10. Vessel has been previously treated and the target lesion is within 5 mm proximal or distal to a previously treated lesion.
11. Target lesion located within an arterial or saphenous vein graft or distal to any arterial or saphenous vein graft.

#### **6.4 Point of Registration**

Lead-In subjects will be considered registered in the trial upon calling IVRS.

During the randomization phase, the subject is considered randomized after IVRS has been called and a device has been assigned (Absorb BVS or XIENCE). The subject is considered registered and in the ITT population at the point of randomization. Once randomization is completed and a treatment arm is assigned, crossover is not permitted. Regardless of the actual device the subject received, the subject will be included in ITT population per the original randomization assignment.

Registered subjects count toward the total sample size in ABSORB III. Refer to **Appendix IV** and **Figures 1 and 2** for further registration details.

#### **6.5 Subject Discontinuation**

Subjects who do not get registered in ABSORB III will be discontinued from the trial.

Missed Visits:

- If a subject misses one or more non-consecutive follow-up contact time points, the visit will be considered a missed visit and subject is not lost-to-follow-up.
- Under extenuating circumstances in which a subject cannot be contacted (e.g serious illness resulting in institutionalization, dementia, incarceration) indirect contact with a subject's healthcare provider or immediate family member identified will not be considered missed visits. Protocol required data will be collected in the electronic case report forms (eCRF). Subject may then return for subsequent visits.

Lost-to-Follow-up:

If the subject misses two consecutive scheduled follow-up time points, and the attempts to contact the subject or subject's healthcare provider or immediate family member detailed below are unsuccessful, then the subject is considered lost-to-follow-up. Site personnel shall make all reasonable efforts to locate and communicate with the subject, including the following, at each contact time point:

- A minimum of two telephone calls to contact the subject should be recorded in the source documentation, including date, time, and initials of site personnel trying to make contact;
- If these attempts are unsuccessful, a certified letter should be sent to the subject.

Subject Discontinuation:

Every subject should remain in the Clinical Investigation until completion of the required follow-up period, however, a subject's participation in any Clinical Investigation is voluntary and the subject has the right to withdraw at any time without penalty or loss of benefit. Conceivable reasons for discontinuation may include, but not be limited to, the following:

- **Subject Withdrawal:** Subject participation in a Clinical Investigation is voluntary and the subject may discontinue participation (refuse all subsequent testing/follow-up) at any time without loss of benefits or penalty.
- **Investigator Termination:** Investigator may terminate the subject's participation without regard to the subject's consent if the Investigator believes it is necessary. Reasons for an investigator's termination of a subject include the following but are not limited to:
  - Per the investigator's discretion, a subject is unable to be compliant with the protocol requirement (e.g., medical conditions such as terminal cancer; subject moved out of the country, etc.)
  - Per the investigator's discretion, the follow-up study requirements (i.e., medications or procedures) may put the subject at risk.
- **Lost-to-Follow-up:** Subject does not complete the scheduled follow-up visits but has not 'officially' withdrawn from the clinical investigation.

Sponsor must be notified of the reason for subject discontinuation. The site will record this information on the eCRF and source documents. Investigators must also report this to their ethics committee (EC) or IRB as defined by their institution's procedure. Subjects will not be replaced.

The subject is considered to have completed the study upon Clinical Investigation completion of the 5-year follow-up.

However, if a subject withdraws from the study due to problems related to the investigational device safety or performance, the investigator shall ask for the subject's permission to follow his/her status/condition outside of the clinical investigation.

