#### **7.4.3 Follow-up Antiplatelet Medications**

All subjects will be maintained at a minimum of 75 mg of clopidogrel daily or 5 or 10 mg of prasugrel daily (10 mg preferred in most patients) or 90 mg twice daily of ticagrelor for a minimum of 12 months following the procedure. For prasugrel subjects  $< 60$  kg in weight or  $\geq 75$  years of age, a maintenance dose of 5 mg per day for 12 months is allowable. Patients with prior stroke or TIA should receive clopidogrel or ticagrelor, not prasugrel. All subjects must receive between  $\geq 75$  to  $\leq 100$  mg of aspirin daily through 5 years follow-up during the study and should continue to take aspirin indefinitely.

Refer to respective prescribing information for ADP antagonist for further details regarding maintenance dose.

The start of anti-platelet medications, any changes or discontinuation of the medications, as well as the reasons for those change will be documented in the eCRF.

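### Section 6.5 lets an investigator end a subject's whole participation over a risky follow-up drug or procedure, with no event follow-up required afterwards: a small, mainly late gap that is cheap to close

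*Combined protocol and SAP*

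**What the plan says.** ABSORB III section 6.5 starts from retention: "Every subject should remain in the Clinical Investigation until completion of the required follow-up period". It then lists reasons for discontinuation, one of which is the investigator's decision: "Investigator may terminate the subject's participation without regard to the subject's consent if the Investigator believes it is necessary". Two of the examples given matter here. One is safety of follow-up: "Per the investigator's discretion, the follow-up study requirements (i.e., medications or procedures) may put the subject at risk". The other is non-compliance, including through illness: "a subject is unable to be compliant with the protocol requirement (e.g., medical conditions such as terminal cancer". After any discontinuation the sponsor is told the reason, the site records it on the eCRF, the ethics committee is informed, and the subject is not replaced.

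Section 6.5 has one provision for follow-up after exit. It applies when a subject withdraws because of device safety or performance: "the investigator shall ask for the subject's permission to follow his/her status/condition outside of the clinical investigation". For subjects who cannot be reached (institutionalised, demented, imprisoned) a milder route exists: "indirect contact with a subject's healthcare provider or immediate family member identified will not be considered missed visits".

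On medication, ABSORB III section 7.4.3 requires a P2Y12 inhibitor for at least 12 months and "aspirin daily through 5 years follow-up during the study and should continue to take aspirin indefinitely". Stops are captured on study: "any changes or discontinuation of the medications, as well as the reasons for those change will be documented in the eCRF". ABSORB IV section 7.4.4 is equivalent. ABSORB III section 16.2 lists bleeding among the common side effects of aspirin.

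**The concern.** The clause treats two decisions as one: stopping a drug or procedure that has become unsafe, and ending collection of outcomes. The first is clinical. The second is not needed for the subject's safety, because asking about events by telephone carries no drug or procedural risk.

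Aspirin is mandatory to year 5, so the medication ground stays available throughout. A subject taken off it for bleeding, or removed for serious illness, may differ in later risk of thrombosis, infarction or death. If participation ends, those later events can go unrecorded, and no analysis recovers events that were never collected.

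Long-term outcome is a stated primary objective of ABSORB IV (section 3). Its section 5.3 lists very late thrombosis and TLF through 5 years on the 4600 subjects of both trials.

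**Working it through.** **1. The plan's own figures.** The plan gives no termination rate. It budgets loss of 5% at 1 year in ABSORB III (1900/0.95 = 2000), and in ABSORB IV 1% at 30 days (2600 × 0.99 = 2574) and 5% at 1 year (2600 × 0.95 = 2470). The Farrington–Manning calculation gives power of 96.3% (stated about 96%), 91.7% (about 92%) and 97.9% (about 98%). These reproduce. No loss allowance for TLF is stated beyond 1 year.

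**2. Does another section restore follow-up?**
- ABSORB III 4.6 keeps registered subjects in follow-up if the trial is discontinued. It does not cover an individual termination.
- ABSORB III 7.5 and ABSORB IV 7.5 require follow-up when no assigned device was implanted. They say nothing about termination.
- The retention default, the indirect-contact rule and the recording of drug stops show that follow-up could continue. None requires it once participation has ended.
- Telephone contact is accepted at every scheduled ABSORB III visit except 1 year, and at every ABSORB IV visit.

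**3. Expected late events.** ABSORB III section 2.2 gives MACE at 1 and 3 years of 6.9% and 8.9% (Absorb Cohort B) and 7.5% and 11.4% (pooled XIENCE V). Used as a proxy for TLF and extended linearly over years 1 to 5:
- (8.9 − 6.9)/2 × 4 = 4.0 points; 4600 × 0.040 = 184 events.
- (11.4 − 7.5)/2 × 4 = 7.8 points; 4600 × 0.078 = 359 events.

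**4. Events unrecorded.** Assume a fraction f = 0.5% to 2% is removed evenly over years 1 to 5, so half the window remains on average, at m = 1 to 3 times the average remaining risk. Remaining risk is r = m × increment/2, from 2.0% (1 × 4.0/2) to 11.7% (3 × 7.8/2).
- Low: 4600 × 0.005 × 0.020 = 0.46.
- High: 4600 × 0.02 × 0.117 = 10.8.
- Share of late events: f × m/2 = 0.25% to 3%.

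**5. Effect on 5-year TLF.** Arms: Absorb 1333 + 1300 = 2633; XIENCE 667 + 1300 = 1967. The planned 1-year rates (7.0% and 9.7%) blend in Absorb to (1333 × 7.0 + 1300 × 9.7)/2633 = 8.33%, so p5 is 12.3% to 16.1%.
- Kaplan–Meier, censoring at exit: shift = −f × (r − increment/2), from 0 (m = 1) to −0.02 × (11.7 − 3.9) = −0.16 points.
- Dropping removed subjects as missing: shift = f × (p5 − r)/(1 − f), from 0.005 × (16.13 − 11.7)/0.995 = +0.02 to 0.02 × (16.13 − 3.9)/0.98 = +0.25 points.
- Equal removal in both arms: at the +0.25 corner XIENCE moves +0.259, so the difference moves by 0.009 points. Removal in Absorb only moves it by at most 0.25.
- 95% half-width of the difference: 1.96 × √[p(1 − p)(1/2633 + 1/1967)] = 1.92 to 2.15 points.

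**6. A harsher model.** Suppose subjects are removed from Absorb only, before any event, with their whole 5-year risk unrecorded at k = 2 to 3 times that of those who stay. The true rate p is assumed to be 15% to 20%. The observed rate is p/(1 − f + kf).
- Mildest: 15/1.005 = 14.93%, a shift of −0.07 points.
- Worst: 20/1.04 = 19.23%, a shift of −0.77 points.

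**7. Very late thrombosis.** Assuming 0.5% to 2% over years 1 to 5, 13 to 53 events are expected in 2633 Absorb subjects. At 1 to 5 times average risk, 2633 × 0.005 × 0.0025 = 0.03 to 2633 × 0.02 × 0.01 × 5 = 2.6 go unrecorded.

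**8. What Version 17.0 could still save.** All 2000 ABSORB III primary-analysis subjects were registered before ABSORB IV opened (ABSORB IV section 1), and an ABSORB IV sub-study subject was enrolled on February 15, 2015 (section 12.1.5). ABSORB III 1-year follow-up therefore ended by about February 2016, 2.5 years before August 16, 2018. Five-year follow-up ends by about February 2020, so at most 1.5 years per subject remained.

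**The case against.** The best defence is that the clause is permissive, hedged and rarely needed. Retention is the default. Every termination is explained to the sponsor and reported to the ethics committee. High bleeding risk and aspirin contraindication are exclusions, drug stops are recorded on study, and ticlopidine may be substituted after intolerance. The 5-year endpoint is summarised descriptively (ABSORB IV 10.4.3). The Kaplan–Meier curves in section 10.4 of both trials keep a subject's data up to exit, so the rule in 10.4.10 that missing data are excluded does not discard everything. The protocol also sends analysis detail to an SAP whose text is not in the pages reviewed, so a by-arm table of discontinuations may already be planned.

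All of this stands, and it lowers the priority. It does not close the gap: a clause that is rarely used still ends event collection when it is used, and Kaplan–Meier cannot supply events after exit.

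It might also be said that procedures do not reach the randomised comparison. That is only partly right. ABSORB-RESOLVe testing was stopped, and the 2000 primary-analysis subjects have no scheduled invasive imaging. But the Imaging Cohort is itself randomised 2:1, and its 3-year angiography with IVUS or OCT is the kind of procedure the clause describes.

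**Conclusion.** The point holds as a small, low-priority design improvement. The reading of the text is firm; the sizes are arithmetic on assumed removal rates and risk multipliers. The late rates are also a proxy: MACE counts all infarctions, Cohort B had 101 subjects with one device size, and years 4 and 5 are extrapolated. Under the main assumptions the 5-year difference moves by at most 0.25 points. The extreme model in step 6 reaches 0.77. Both are below the half-width of about 2 points. The sign depends on the analysis method, so the direction of any bias is unknown.

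Three stronger readings are tempting, and the documents do not support them.
- **That the primary results are threatened.** The 30-day endpoint leaves little time for such removals. If 1% to 2% of the Absorb arm alone were lost at 2 to 3 times the risk, the one-sided error of the ABSORB III test at its margin would rise from 2.5% to between 3.1% and 5.3%. Nothing indicates one-sided removal. By ABSORB IV's planning rates, 4.9/9.7 = 51% of first-year TLF falls by day 30, and ABSORB III 1-year follow-up was over before this version.
- **That exposure is confined to late follow-up.** The P2Y12 requirement covers the first 12 months, so bleeding-related removals could also occur then. Mainly late is as far as the text goes.
- **That recoverable ABSORB IV follow-up can be calculated.** The two dates in section 12.1.5 are the first sub-study enrolment and a sub-study status date. They are not the parent trial's enrolment limits, so no figure can be derived.

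**What to change.** Amend ABSORB III section 6.5, and through it ABSORB IV section 6.5. Where a follow-up medication or procedure may endanger the subject, or a medical condition prevents compliance, the investigator stops only the medication or procedure concerned. The subject stays in the study for event and vital-status follow-up, by telephone or by extending the indirect contact already allowed, unless the subject withdraws consent. Report investigator terminations by arm, with the reasons already on the eCRF, beside the 5-year results.

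The cost is one wording amendment with its ethics review, one table from data already collected, and a few extra contacts by existing site staff. For an Imaging Cohort subject the change preserves clinical follow-up. It cannot recover a 3-year image that was rightly not taken, and section 10.3.2 already assumes only 50% imaging follow-up in that cohort.
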